We have used this approach—primarily phone-based administration of instruments by highly trained VA employees with substantial support, understanding of Veterans' issues, and of VA safety protocols—successfully in VA Ann Arbor studies including ResCU 1, ResCU 2 (IIR's 13-079 and 17-045, Protocols 1597244 and 1597246).

We will minimize total survey error by random sampling from a group of Veterans known from the VA's CDW to ensure very high recruitment and retention rates—our group routinely exceeds recruitment rates of 80% in studies of recently critically ill patients or Veterans, with whom we have conducted over 4,000 interviews, including among individuals with substantial disability and cognitive impairment.⁴⁶ These high recruitment, retention, and survey completion rates have been achieved through careful attention to detail, stable diverse staff (some of whom are Veterans) in whom we invest in ongoing training, and with whom we engage in constant refinement of methods. These methods (including survey practices, personnel training, and customized database organization built in VA REDCap and integrated into staff calendaring and email) have been codified as Standard Operating Procedures upon which we will build.

REDCap: VA REDCap (Research Electronic Data Capture) is a web-based application hosted and maintained by the VA Informatics and Computing Infrastructure (VINCI) and VA Information Resource Center (VIReC). It is housed on a VINCI server physically located at the VA Austin Information Technology Center (AITC) in Austin, Texas and is available only on the VA network. REDCap data collection and management projects rely on a thorough study-specific data dictionary defined in an iterative self-documenting process. This includes a study-specific user rights management system administered by the Project Owner or Principal Investigator. REDCap (www.project-redcap.org) was developed specifically around HIPAA-Security guidelines. REDCap has been disseminated for use locally at other institutions and currently supports 1,700+ academic/non-profit consortium partners on six continents and over 305,000 research end-users.

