Statistical Analysis Plan

COVID-19 Observational Research Collaboratory
NCT05394025

Updated: June 25, 2025

Background

In a previous study, we found Veterans with a first case of COVID-19 (between 2020 and 2021) did not report more limitations in instrumental activities of daily living (IADL) at 18-months after infection relative to comparators who were contemporaneously uninfected.

Aim

In this updated longitudinal analysis, we examine whether self-reported counts of IADL changed between infected and uninfected comparators over 18 additional months of follow-up (36 months after infection).

Study Design

Prospective cohort study design with repeated surveys at 18-, 24-, 30-, and 36- months.

Population

The cohort was sampled from a parent cohort of Veterans, assembled by the COVID-19 Observational Research Collaboratory, with a first documented case of COVID-19 between March 2020 and April 2021 and uninfected matched comparators. Veterans were required to have been enrolled in VHA care, been assigned a VA primary care team, and had one or more VA primary care visits in the two years prior to cohort construction. COVID-19 infections were ascertained through the VA COVID-19 Shared Data Resource (CSDR) and Medicare claims data. Otherwise, eligible Veterans without evidence of a documented infection were considered as uninfected comparators. From this parent cohort, we conducted a stratified random sample of 100 Veterans who tested positive for COVID-19 in October, November, December, February, March, and April 2021. Sampling was further stratified by US Census region and hospitalization status. Of the 600 patients with COVID-19 a total of 235 (39.2%) Veterans consented and completed surveys; 244 uninfected matched comparators completed surveys.

Exposure

First documented COVID-19 infection (positive PCR test or clinical note) was the primary exposure of interest. Veterans without a documented history of COVID-19 infection were eligible comparators. Extensive matching, done monthly, was used to ensure comparability between groups.

Outcome

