Self-reported IADL limitations were the primary outcomes of interest. The IADL instrument was initially administered at 18-months after infection (or matched index date) and was subsequently readministered three additional times 6 months apart. The IADL asks respondents whether they experienced difficulties or limitations with daily activities and functions such as with "walking across a room" or "shopping for groceries." We report individual IADL responses but use a cumulative count of self-reported limitations (0-14) as our primary IADL score as an outcome.

Analysis

We used descriptive statistics to compare the Veterans with COVID-19 and comparators. A table of frequencies was generated to compare IADL item responses between groups at each time point. We used a linear mixed model with random intercept (respondent) and slope (survey cycle time) to assess differences in the change in IADL scores. The model included terms for age, sex, and Care Assessment Needs (CAN) score to adjust for potential important confounders. An interaction term between COVID-19 status and time was included to assess whether changes in IADL scores over time differed between the COVID-19 and comparator groups. We used a likelihood ratio test to test for statistical significance and report 95% confidence intervals for all reported model coefficients.

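### Age, sex and CAN, entered as time-fixed main effects, do not adjust the COVID x time term on which the inference about change rests

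*SAP*

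**What the plan says.** The SAP's Analysis section fits a linear mixed model to the IADL count (0-14), with a random intercept and a random slope on survey cycle, over surveys at 18, 24, 30 and 36 months. On confounding it states: "The model included terms for age, sex, and Care Assessment Needs (CAN) score to adjust for potential important confounders". On the question of change: "An interaction term between COVID-19 status and time was included to assess whether changes in IADL scores over time differed". That is the only interaction named. The model is not written out, the terms dropped in the likelihood ratio test are not named, and nothing says when CAN was measured or whether it was updated.

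The other protection against confounding is the design. SAP, Exposure: "Extensive matching, done monthly, was used to ensure comparability between groups". The SAP does not list the matching variables. Protocol 5.1 (Comparators) leaves the choice between coarsened exact matching and propensity scores open.

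On who is analysed, SAP, Population says: "Of the 600 patients with COVID-19 a total of 235 (39.2%) Veterans consented and completed surveys", and "244 uninfected matched comparators completed surveys". The number of comparators approached is not given. Protocol 5.1 had argued from past experience that "our group routinely exceeds recruitment rates of 80% in studies of recently critically ill patients or Veterans".

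**The concern.** The SAP gives three covariates the job of controlling confounding, and its question is about change. A time-fixed main effect moves a respondent's whole trajectory up or down. It does not alter that respondent's slope, so it cannot remove a slope difference that arises because one group is older or has higher CAN scores. A reader would take the reported COVID x time coefficient to be adjusted for age, sex and CAN when it is not.

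Control of slope confounding by these variables then rests on the matching alone. Matching that succeeded would protect slope as well as level, but it was done in the parent cohort and the analysis uses respondents. With 39.2% of sampled cases taking part and comparator participation unknown, balance among respondents is not assured. If the planned descriptive comparison shows a gap in age, sex or CAN, the model as described cannot correct the slope difference for it.

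**Working it through.** **Inputs.** From the SAP: 235 cases, 244 comparators, four equally spaced surveys, random intercept and slope. As a check on its one relevant figure, 235/600 = 39.2%, as stated. Assumed, because the documents give none of them: residual variance 1.5; random-slope variance 0.15 net of CAN; two-sided test at 0.05; the CAN gap between groups; and the CAN effect on slope.

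**Step 1: the structure.** Code time 0, 1, 2, 3, so that the sum of squares about its mean is 5. With complete data, COVID x time is the difference in mean per-respondent slopes. A time-fixed covariate enters only the intercept equation and drops out of the slope equation.

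Full maximum-likelihood fits to three simulated data sets (CAN gap 0.2 SD, slope effect 0.089, complete data) gave:

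| Data set | No covariates: estimate (LRT) | With age, sex, CAN main effects | With covariate x time terms |
|---|---|---|---|
| 1 | 0.05198 (0.8079) | 0.05198 (0.8079) | 0.03857 |
| 2 | -0.00883 (0.0204) | -0.00883 (0.0204) | -0.02024 |
| 3 | 0.13372 (4.6178) | 0.13372 (4.6178) | 0.10395 (2.7995) |

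In the third data set p moved from 0.032 to 0.094, and only when the covariate x time terms were added. A separate fit under slightly different assumed variances gave 0.020037 with and without the main effect, and -0.0253 with covariate x time.

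**Step 2: dropout.** With 72-78% retained at 36 months, main effects moved the three estimates by 0.0003, 0.0001 and 0.0021. Over 2,000 replicates at about 75% retained, the shift averaged 0.003 and was at most 0.017, against an SE of 0.068. Mean bias with no covariates / main effects / covariate x time was 0.0189 / 0.0192 / 0.0018 (gap 0.2 SD, slope effect 0.089) and 0.0600 / 0.0605 / 0.0016 (0.3 SD, 0.20). The main effects remove none of it.

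**Step 3: size.** Let b be the CAN effect on slope per SD per cycle, and g the gap in SD.

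- Bias per cycle = g x b. Over 18 months (three cycles) it is 3 x g x b.
- SE = sqrt((0.15 + b² + 1.5/5) x (1/235 + 1/244)), which is 0.0613 at b = 0.
- Share of slope variance = b²/(b² + 0.15).
- Type I error = P(|Z + bias/SE| > 1.96).

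Worked cell: b = 0.089, g = 0.2. Bias = 0.0178, SE = 0.0618, ratio 0.288, so the error is 4.7% + 1.2% = 6.0% (5.95% before rounding).

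| b (share of slope variance) | gap 0.1 SD | gap 0.2 SD | gap 0.3 SD |
|---|---|---|---|
| 0.055 (2%) | 5.1% | 5.4% | 5.8% |
| 0.089 (5%) | 5.2% | 6.0% | 7.2% |
| 0.15 (13%) | 5.7% | 7.6% | 11.1% |
| 0.20 (21%) | 6.1% | 9.6% | 15.5% |

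Bias over 18 months runs from 3 x 0.1 x 0.055 = 0.02 to 3 x 0.3 x 0.20 = 0.18 limitations. Simulated likelihood ratio tests (20,000 replicates) agree: for example 6.0% at 5% x 0.2 SD and 15.8% at 21% x 0.3 SD. With CAN x time in the model the rate was 4.9-5.3% throughout.

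**Step 4: could such a gap arise?** By chance, ignoring matching, the gap has SD sqrt(1/235 + 1/244) = 0.091. Gaps above 0.1 / 0.2 / 0.3 SD then have probability 27.4 / 2.9 / 0.1%. Averaged over chance gaps the test keeps its level (5.1% simulated), so inflation needs response that depends on CAN differently in the two groups. If comparator response does not depend on CAN, and case response follows a logistic model in standard normal CAN, the odds ratios per SD that produce these gaps are:

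| Case participation | 0.1 SD | 0.2 SD | 0.3 SD |
|---|---|---|---|
| 39.2% | 1.18 | 1.40 | 1.69 |
| 80% | 1.68 | 3.41 | 19.7 |

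If both groups respond to CAN alike at similar participation, no gap arises.

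**The case against.** **No harm is shown.** This stands. The larger figures need a 0.3 SD gap, which chance would almost never produce, together with a strong CAN effect on slope. At modest inputs the error is 5.1-6.0%. The odds ratios assume that comparator response is unrelated to CAN, and nothing in the documents says that the groups responded differently. The 80% figure describes past studies, and its denominator may differ.

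**Matching is the design's main control.** It is, and the variables may be documented with the parent cohort. But adding model covariates as confounders implies that matching was not thought sufficient by itself, and Protocol 5.1 likewise planned covariate adjustment on top of matching for causal effects.

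**The SAP does not say which terms the likelihood ratio test drops.** True. Under a joint 2-df test of COVID and COVID x time, main effects do change the statistic (in two simulated data sets, from 0.29 to 0.005 and from 0.84 to 3.38). The 1-df reading follows from the interaction's stated purpose, and the COVID x time coefficient and its interval stay unadjusted under either test.

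**The text is a short summary.** Covariate x time terms may have been fitted and not described, or CAN re-measured at each survey. In the first case the point falls away. In the second the algebra no longer applies, but CAN measured after infection may lie on the causal path.

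**The main effects still do work.** They do: they adjust the level difference, which is also reported. They do not adjust the comparison of change that is the SAP's aim.

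**Conclusion.** The concern holds. Confidence is high that time-fixed main effects leave the slope contrast unadjusted: this is exact with complete data and close to exact with dropout. Confidence is medium that the SAP's covariates are main effects only, since the model is not written out. Confidence is low that bias is present, because the documents give neither the balance among respondents nor any covariate effect on slope.

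The likely size is small under modest assumptions and material only if a sizeable gap and a strong slope effect occur together. It should be fixed because the stated purpose of the covariates and the tested term do not match, and the remedy is cheap. It is not a finding that the results are wrong.

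**What to change.** - Write out the model and the pair of nested models compared in the likelihood ratio test.
- State when CAN was measured, and use a value from before the index date. Protocol 5.7 gives two extraction times for Aim 1 predictors (testing and hospitalization) and does not say which applies here.
- Add age x time, sex x time and CAN x time. Report the COVID x time estimate, interval and test from that model beside those from the present one.
- In the descriptive comparison already planned, give standardized differences among respondents for age, sex and CAN, and list the matching variables.

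**Cost.** Three fixed effects on data already held, assuming a linear covariate effect on slope. The SE of COVID x time rises by 0.3% with no gap, 1.0% with 0.2 SD gaps in age and CAN, and 1.9% with 0.3 SD gaps (0.4, 1.1 and 2.0% with dropout). These figures assume an age-CAN correlation of 0.4 and 10% in the smaller sex group.

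The change is also late. Sampling was a "stratified random sample of 100 Veterans who tested positive for COVID-19 in October, November, December, February, March, and April 2021", so the last 36-month survey falls about April 2024, some 14 months before the SAP's date ("Updated: June 25, 2025"). If the present model has already been run on the outcome data, label the added terms as introduced after follow-up and show both results with equal prominence.
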